7.5 Medical History and Concurrent Medical Conditions

Medical history and concurrent medical conditions will be coded using the latest MedDRA dictionary. Concurrent medical conditions are the ones ongoing or started on or after the day informed consent was signed. Medical history and concurrent medical conditions will be summarized separately by safety analysis set for Part 1 escalation cohorts and Part 2 expansion cohorts and by full analysis set for Part 3 extension cohorts.

If both start date and stop date are missing, medical condition will be assumed to start before informed consent and continue after treatment discontinuation. If only start date is missing, then medical condition will be assumed to start before informed consent. If stop date is missing, then medical condition will be assumed to continue after treatment discontinuation.

7.6 Medication History and Concomitant Medications

Medication history and concomitant medications will be coded using the latest World Health Organization (WHO) Drug Dictionary. Medication history is defined as the medication stopped before the first dosing date of the study drug. Concomitant medication is defined as the medication ongoing or started on or after the first dosing date of the study drug. Medication history and concurrent medications will be summarized separately by safety analysis set for Part 1 escalation cohorts and Part 2 expansion cohorts and by full analysis set for Part 3 extension cohorts. The number and percentage of patients taking concomitant medications will be tabulated by WHO standardized medication name.

If both start date and stop date are missing, medication will be assumed to start before the first dosing date of the study drug and continue after treatment discontinuation. If only start date is missing, then medication will be assumed to start before the first dosing date of the study drug. If only stop date is missing, then medication will be assumed to continue after treatment discontinuation.

7.7 Study Drug Exposure and Compliance

Summaries and descriptive statistics of duration of treatment with modakafusp alfa (in weeks for Parts 1 and 2, and months for Part 3), number of treated cycles (1, 2, 3, 4, 5, 6, 7-12, >12 and summary statistics), cumulative dose, planned cumulative dose (Part 3 only), actual and planned dose per cycle, and relative dose intensity will be summarized by safety analysis set in Part 1 escalation cohorts and Part 2 expansion cohorts and by full analysis set for Part 3 extension cohorts. A treated cycle is defined as a cycle in which any amount of modakafusp alfa for at least one of the dosing days in the cycle. Dose unit will be mg/kg for Part 1/Part 2 and mg for Part 3.

The algorithm details will be documented in the analysis dataset specifications.

Action on Study Drug

The reason for dose modification (e.g. dose increased, dose reduced, interrupted, withdrawn, delayed, rate increased, rate reduced, drug infusion interrupted) of modakafusp alfa will be summarized by cycle (Cycles 1-8), greater than 8 cycles and overall.

7.8 Efficacy Analysis

7.8.1 Part 1 and Part 2 Efficacy Analysis

Response evaluations after the start of subsequent anti-cancer therapy will not be considered in the calculation of efficacy endpoints, while the response evaluation after the treatment discontinuation will be considered in the calculation of efficacy endpoints. Please refer to Section 7.9.2 Part 3 Efficacy Analysis for details. When appropriate, data from patients in the

expansion cohorts will be summarized together with data from patients in the dose escalation phase.

Objective Response Rate (ORR)

The ORR is defined as the proportion of patients who achieved a confirmed PR or better during the study per investigator assessment as defined by IMWG Uniform Response Criteria. The ORR will be summarized by frequencies, percentages, and the exact two-sided 95% CIs based on the safety analysis set.

Clinical Benefit Rate (CBR)

The CBR includes patients with a confirmed response of sCR, CR, VGPR, PR, or MR during the study per investigator assessment as defined by IMWG Uniform Response Criteria. The CBR will be summarized by frequencies, percentages, and the exact two-sided 95% CIs based on the safety analysis set.

Disease Control Rate (DCR)

The DCR includes patients with a confirmed response sCR, CR, VGPR, PR, MR, or SD during the study per investigator assessment as defined by IMWG Uniform Response Criteria. The DCR will be summarized by frequencies, percentages, and the exact two-sided 95% CIs based on the safety analysis set.

Duration of Response (DOR)

The DOR will be calculated for those patients with a confirmed PR or better in the safety analysis set. The DOR is defined as the time from the first documentation of a confirmed response until progressive disease or death, whichever comes first. If there is no progressive disease or death observed, it will be censored at the last adequate response assessment. Please refer to Table 1 for the detailed censoring rules.

DOR (months) = (date of progression/death or censor – date of confirmed response + 1)/30.4375. The Kaplan-Meier method will be used to estimate the distribution of DOR. The Kaplan-Meier survival curves, 25th, 50th (median), and 75th percentiles, along with the associated 2-sided 95% confidence intervals (CIs) based on Brookmeyer and Crowley method, and Kaplan-Meier probability estimates with 95% CIs at 6 and 12 months (or later time points if data permits) will be presented. The number of patients with events and the number of patients censored will be summarized.

Progression Free Survival (PFS)

PFS is defined as the time from the date of first dose to the date of the first documentation of a confirmed PD per IMWG criteria, or the date of death due to any cause, whichever occurs first. Patients without documentation of confirmed PD or death will be censored at the date of the last adequate response assessment prior to the date of initiation of subsequent anti-cancer therapy. Patients with no post baseline response assessment will be censored on day 1, unless patient died without extended loss-to-follow-up time. Please refer to Table 1 for the detailed censoring rules.

PFS (months) = (earliest date of progression or death or censor – date of first dose + 1)/30.4375. The analysis of PFS will be based on safety analysis set. The Kaplan-Meier method will be used to estimate the distribution of PFS. The Kaplan-Meier survival curves, the 25th, 50th (median), and 75th percentiles, along with associated 2-sided 95% confidence intervals (CIs) based on Brookmeyer and Crowley method, and Kaplan-Meier PFS probability estimates with 95% CIs at 3 and 6 months (or later time points if data permits) will be presented. The number of patients with events along with the type of events (death or progressive disease) and the number of patients censored will be summarized.

Time to Response (TTR)

Time to response is defined as the time from first dose to the date of first documentation of confirmed response (PR or better). Patients without confirmed response will not be included in the analysis of TTR.

TTR (months) = (date of confirmed response – date of first dose + 1)/30.4375).

Descriptive statistics including mean, median, standard deviation, minimum, maximum, Q1 and Q3 will be summarized in responders.

In addition, time to the best response (the time from the first dose to the date of the first documentation of the best confirmed response [PR or better]) will be analyzed by using the same approach.

Overall Survival (OS)

Overall survival is defined as the time from the date of first dose to the date of death from any cause. Patients without documentation of death at the time of analysis will be censored at the date last known to be alive.

OS (months) = (date of death or censor – date of first dose + 1)/30.4375

The analysis of OS will be based on safety analysis set. The Kaplan-Meier method will be used to analyze the distribution of OS. Kaplan-Meier survival curves, the 25th, 50th (median), and 75th percentiles, along with the associated 2-sided 95% CIs based on Brookmeyer and Crowley method, and Kaplan-Meier estimates with 95% CIs at 6 and 12 months (or later time points if

data permits) will be presented. The number of patients with events and the number of patients censored will be summarized.

Best Overall Response

Best overall response is defined as the best response recorded after the first dose of study drug until subsequent anti-cancer therapy.

Confirmation of Response: All response categories except SD (sCR, CR, VGPR, PR, PD) require 2 consecutive adequate assessments made at any time before the initiation of subsequent anti-cancer therapy. There is no requirement on the time interval between the two visits.

Consecutive visits are needed for response confirmation, except if there is one or two “not evaluable” (NE) or “not done” (ND) assessments in between.

Either one or two consecutive occurrences of “ND” or “NE” between responses can be skipped when confirming a response such as:

PR -> NE -> PR: PR is considered to be confirmed in this case.

CR -> ND -> CR: CR is considered to be confirmed in this case.

Confirmation of PD:

1. If only one PD is recorded as the last available assessment prior to the subsequent anti-cancer therapy, it can be counted as a confirmed PD. It will be considered as an event for DOR, TTP, PFS analyses.

BL → SD → PD → Subsequent anti-cancer therapy/End – It is a confirmed PD

2. If only one PD value is recorded in the middle of responses better than PD as below, it will not be counted as a confirmed PD. It will not be considered as an event for DOR, TTP, PFS analyses.

BL → SD → PD → SD → SD → Subsequent anti-cancer therapy/End – It is not a confirmed PD.

3. If the PD is due to imaging (plasmacytomas or bone lesion), the PD can be considered as a confirmed PD.

4. If only one PD is recorded as the last available assessment before the patient discontinues the treatment due to PD, it can be counted as a confirmed PD.

Best M-Protein Response

The best m-protein response is defined as the percent change from baseline to the best (lowest) value post-baseline. For subjects with both measurable serum and urine m-protein at baseline, the best m-protein will be the worse (i.e. lower percent reduction) of the best serum m-protein and the best urine m-protein. For subjects with only measurable serum m-protein at baseline, the

CONFIDENTIAL

best m-protein response is based on serum m-protein. For subjects with non-measurable serum m-protein at baseline, but measurable urine m-protein at baseline, the best m-protein response is based on the urine m-protein. If not measurable by serum or urine m-protein the best m-protein response is based on the difference between involved and unininvolved FLC. A waterfall plot of the best m-protein response will be generated. The plot will have the following information:

1. Response.
2. Dose.
3. Schedule.
4. Measurable categories: Both Serum and Urine M-protein/Serum M-protein/Urine M-protein/FLC.

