- c) Serum free light chain (FLC) assay with involved FLC level ≥10 mg/dL (≥100 mg/L) provided serum FLC ratio is abnormal.
- 4. During Part 1 only, patients not meeting the above criteria for measurable disease should, at least, have measurable bone marrow plasmacytosis (≥10%) and/or plasmacytoma (≥1 cm in diameter) detected by physical examination or imaging.
- 5. ECOG performance status of ≤ 2 .
- 6. Patient has adequate organ function as determined by the following laboratory values.

Absolute neutrophil count ^a	$\geq 1000/\text{mm}^3 (\geq 1.0 \times 10^9/\text{L})$
Platelets ^a	≥75,000/mm³ (≥75×10°/L)
Hemoglobin	≥75 g/L
Creatinine clearance	≥30 mL/min (Cockcroft-Gault)
Total serum bilirubin	<2.0×ULN; an exception for patients with Gilbert's syndrome may be granted after discussion with the sponsor.
Liver transaminases (ALT/AST)	≤3.0×ULN

ALT: alanine aminotransferase; AST: aspartate aminotransferase; ULN: upper limit of the normal range.

7. Female patients who:

- Are postmenopausal for at least 2 years before the screening visit, OR
- Are surgically sterile, OR
- If they are of childbearing potential:
 - Agree to practice 1 highly effective method of contraception and 1 additional effective (barrier) method at the same time, from the time of signing the informed consent through 7 days after the last dose of study drug, OR
 - Agree to practice true abstinence, when this is in line with the preferred and usual lifestyle of the subject, from the time of signing the informed consent through 7 days after the last dose of study drug. (Periodic abstinence [eg, calendar, ovulation, symptothermal, postovulation methods], withdrawal, spermicides only, and lactational amenorrhea are not acceptable methods of contraception. Female and male condoms should not be used together.)
 - Agree not to donate an egg or eggs (ova) during the study and for 7 days after the last dose of study drug.
- 8. Male patients, even if surgically sterilized (ie, status post vasectomy), who:
 - Agree to practice effective barrier contraception during the entire study treatment period and through 7 days after the last dose of study drug, OR
 - Agree to practice true abstinence, when this is in line with the preferred and usual lifestyle of the subject. (Periodic abstinence [eg, calendar, ovulation, symptothermal,

^a Without ongoing growth factor or transfusion support for at least 1 week before Day 1.

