VGPR	Serum and urine M-protein detectable by immunofixation but not on electrophoresis, or ≥90% reduction in serum M-protein plus urine M-protein <100 mg/24 hours; in patients for whom only measurable disease is by serum FLC level, >90% decrease in difference between involved and uninvolved FLC levels, in addition to VGPR criteria, is required; 2 consecutive assessments are needed °.
PR	≥50% reduction of serum M-protein and reduction in 24-hour urinary M-protein by ≥90% or to <200 mg/24 hours.
	If the serum and urine M-protein are not measurable, a ≥50% decrease in the difference between involved and uninvolved FLC levels is required in place of the M-protein criteria.
	If serum and urine M-protein are not measurable, and serum FLC is also not measurable, ≥50% reduction in bone marrow plasma cells is required in place of M-protein, provided the baseline percentage was ≥30%.
	In addition to the above criteria, if present at baseline, ≥50% reduction in the size of soft tissue plasmacytomas is also required.
	Two consecutive assessments are needed ^a no known evidence of progressive or new bone lesions if radiographic studies were performed.
MR ^b	≥25% but ≤49% reduction of serum M-protein and reduction in 24-hour urine M-protein by 50% to 89%.
	In addition to the above criteria, if present at baseline, 25% to 49% reduction in the size of soft tissue plasmacytomas is also required.
	No increase in size or number of lytic bone lesions (development of compression fracture does not exclude response).
SD °	Does not meet the response criteria for CR (any variant), VGPR, PR, MR, or PD; no known evidence of progressive or new bone lesions if radiographic studies were performed.
PD	See text below.

BM: bone marrow; CR: complete response; FLC: free light chain; MR: minimal response; ORR: objective response rate; PR: partial response; PD: progression of disease; RRMM: relapsed refractory multiple myeloma; sCR: stringent complete response; SD: stable disease; VGPR: very good partial response.

^a Clonality should be established by showing κλ light-chain restriction on flow cytometry, immunohistochemistry, or immunofluorescence. Bone marrow plasma cell percentage should preferably be estimated from a core biopsy specimen; in case of a disparity between the aspirate and core biopsy, the highest value should be used. For this

Response	
Category	Response Criteria

trial 2 consecutive BM assessments are not required.

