5.1.2 Part 1 Secondary Endpoints

- DLT-like (TEAEs meeting DLT definition that occur after phase 1 Cycle 1) frequencies and other TEAEs occurring over the course of extended treatment with modakafusp alfa, including information about dose modification, treatment discontinuation, and clinically significant laboratory values and vital signs
- Summary statistics by dose level and cycle day for the following PK parameters:
 - Single-dose maximum observed concentration (C_{max}).
 - Time of first occurrence of C_{max} (t_{max}).
 - Area under the serum concentration-time curve from time 0 to infinity (AUC_{∞}).
 - Area under the serum concentration-time curve from time 0 to time of the last quantifiable concentration (AUC_{last}).
 - Apparent serum modakafusp alfa terminal disposition rate constant (λ_z).
 - Apparent serum modakafusp alfa terminal elimination phase half-life ($t_{1/2z}$).
 - Total clearance after administration (CL).
 - Volume of distribution at steady state (V_{ss}).
- Anti-modakafusp alfa antibody incidence and characteristics (eg, titer and specificity), neutralizing antibody (NAb).
- Preliminary evaluation of antitumor activity of modakafusp alfa:
 - For patients with measurable disease only: ORR, defined as the proportion of patients who achieved a PR or better during the study: stringent complete response (sCR), complete response (CR), very good partial response (VGPR), and PR as defined by IMWG Uniform Response Criteria; CBR (includes patients with a response of sCR, CR, VGPR, PR, or minimal response [MR]); DCR (includes patients with a response of sCR, CR, VGPR, PR, MR, or stable disease [SD]).

- For patients with measurable disease only: median DOR, with DOR defined as the time from the date of first documentation of response PR or better to the time of disease progression or death, whichever occurs first.
- For patients with measurable disease only: time to response, defined as the time from first dose to the date of first documentation of response (PR or better).
- PFS, defined as the time from the date of first dose until the sooner of the date of PD, defined by IMWG criteria, or the date of death due to any cause.

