Duration of disease control is defined as the time from first documented evidence of SD or better until the earliest date of a confirmed PD per IMWG, or death among patients who achieve a SD or better. Patients without confirmed PD or death will be censored at the censoring time point for PFS as specified in Table 1.

Duration of disease control will be analyzed at the time of primary ORR analysis, also at final analysis (study close out), based on responses assessed by both IRC and investigator.

Duration of disease control will be summarized using the Kaplan-Meier method by dose level for patients with a SD or confirmed MR or better. Median duration of disease control, first and third quartiles and 95% CI, will be estimated using the Brookmeyer-Crowley method.

PFS

PFS is defined as the time from the date of first dose until the earliest date of confirmed PD per IMWG, or death due to any cause. PFS will be analyzed at the time of primary analysis of ORR, also at final analysis (study close out), based on responses assessed by both IRC and investigator.

A summary of the assignments for progression and censoring dates for PFS are specified in Table 1 below.

Table 1 Assignments for Progression and Censoring Date for PFS Analysis

Scenarios	Event date/censoring date	Event status
No (or inadequate) baseline tumor assessments ¹	Date of the first dose	Censored
No post-baseline assessments	Date of the first dose	Censored
Confirmed progression documented without extended loss-to-follow-up time (two or more missed cycles) ⁴	Date of assessment of the earliest date of the confirmed progression	Event
No confirmed progression or death	Date of last adequate assessment of response ²	Censored
Subsequent anti-cancer therapy started (before documented confirmed progression or death) ³	Date of last adequate assessment of response ² (prior to the initiation of the subsequent anti-cancer therapy)	Censored
Death without extended loss-to-follow-up time	Death date	Event
Death or progression after an extended loss-to-follow-up time (two or more missed cycles) ⁴	Date of last adequate assessment of response ² (prior to missed assessments)	Censored

1. Adequate baseline assessment is defined as at baseline, a patient has at least one of the following measurements:
 - a. Serum M-protein $\geq 0.5\text{g/dL}$ ($\geq 500\text{ mg/dL}$) or
 - b. Urine M-protein $\geq 200\text{ mg/24 hours}$ or

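### Part 1 ORR, DOR and TTR are analysed without the measurable-disease limit in their endpoint definitions, while PFS, which has no such limit, meets a censoring row that can remove the same patients at first dose

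*SAP*

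**What the plan says.** **Eligibility.** Protocol 7.1, criterion 4: "During Part 1 only, patients not meeting the above criteria for measurable disease should, at least, have measurable bone marrow plasmacytosis" of 10% or more, and/or a plasmacytoma of at least 1 cm. Parts 2 and 3 require measurable disease (criterion 3).

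**Response endpoints.** SAP 5.1.2, matching Protocol 5.4.1.2: "For patients with measurable disease only: ORR, defined as the proportion of patients who achieved a PR or better during the study". DOR and time to response carry the same opening restriction. CBR and DCR stand in the ORR bullet in both sections, but the protocol synopsis lists them as separate Part 1 bullets without it.

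**Response analysis.** SAP 7.8.1, for Parts 1 and 2 together: "The ORR will be summarized by frequencies, percentages, and the exact two-sided 95% CIs based on the safety analysis set". CBR and DCR use the same set. DOR is computed for all confirmed responders in that set, and TTR has no measurable-disease limit. SAP 7.1 makes the analysis-set count the denominator, and SAP 7.2 confirms that the safety set also serves efficacy in these parts.

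**PFS and DOR censoring.** The Part 1 PFS endpoint is not limited to measurable disease. SAP 7.8.1 sends both PFS and DOR to Table 1 (SAP 7.8.2.2) for detailed rules. The first row of that table, "No (or inadequate) baseline tumor assessments", is censored at the date of first dose. Footnote 1 explains: "Adequate baseline assessment is defined as at baseline, a patient has at least one of the following measurements", and then lists the serum M-protein, urine M-protein and FLC thresholds that define measurable disease.

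**The concern.** The endpoint definitions and the analysis section treat the same Part 1 patients in opposite ways. For ORR, DOR and TTR the endpoint leaves them out and the analysis takes them in. For PFS the endpoint takes them in and one row of the censoring table leaves them out.

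For ORR, the extra patients have fewer routes to response. With no measurable M-protein or FLC, PR goes through marrow: "≥50% reduction in bone marrow plasma cells is required in place of M-protein, provided the baseline percentage was ≥30" per cent. A patient who entered with 10 to 29% marrow plasma cells does not meet that condition.

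For PFS, progression in these patients can be observed. Appendix F has a marrow route to PD for patients without measurable M-protein or FLC, and counts new or enlarging plasmacytomas. SAP 7.8.1 accepts PD on imaging as confirmed. Censoring at first dose would discard such events.

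At stake are the Part 1 activity estimates by dose level, where denominators are small, and any summary that pools escalation with expansion, which SAP 7.8.1 allows. Two programmers working from this SAP could also produce different PFS and DOR results.

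**Working it through.** **1. The one pooled figure in the documents.** SAP 7.13 gives an ORR of 40% in 30 patients treated at 1.5 mg/kg, escalation plus expansion. Protocol 4.6.2 gives 44% of 25 in expansion and 1 PR among 5 in escalation at that dose Q4W.
- 0.44 × 25 = 11 responders; (11 + 1)/(25 + 5) = 12/30 = 40.0% (exact 95% CI 22.7 to 59.4).

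The figure reproduces with all 5 escalation patients in the denominator.

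**2. Removing non-measurable patients.** The documents do not say how many there were. Assume that k of the escalation patients in a cell were non-measurable and did not respond. The ORR under the endpoint definition is responders/(n − k).

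| Cell | k = 0 | k = 1 | k = 2 |
|---|---|---|---|
| 1.5 mg/kg Q4W, escalation | 1/5 = 20% | 1/4 = 25% | 1/3 = 33% |
| 3 mg/kg Q4W, escalation | 2/7 = 29% | 2/6 = 33% | 2/5 = 40% |
| 1.5 mg/kg, pooled | 12/30 = 40.0% | 12/29 = 41.4% | 12/28 = 42.9% |

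At the extreme of k = 4, the pooled figure is 12/26 = 46.2% (26.6 to 66.6).

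**3. Part 1 as a whole.** If m of N patients are non-measurable and none responds, the safety-set ORR is the measurable-disease ORR times (N − m)/N. With the planned 36 to 51 evaluable patients:
- N = 36: 35/36 = 0.97 for m = 1; 31/36 = 0.86 for m = 5.
- N = 51: 50/51 = 0.98 for m = 1; 46/51 = 0.90 for m = 5.

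**4. Knock-on to Part 3.** The 40% sets the mean of the Beta(1.2, 1.8) prior for the 120 mg arm. A beta-binomial calculation (success at 33 or more of 118, stop if predictive probability is below 10%) reproduces the stated boundaries of ≤1 of 15 and ≤10 of 48. For k from 0 to 4 the first boundary does not move. With prior weight held at 3 patients, the second stays at ≤10 for k ≤ 1 and becomes ≤9 for k = 2 to 4. With weight scaled to 10% of (30 − k), it becomes ≤9 only at k = 4.

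**5. PFS, provisions side by side.** For a non-measurable patient with confirmed PD or a timely death:
- Table 1, first row with footnote 1: censored at first dose.
- Table 1, rows for confirmed progression and for death, each without extended loss to follow-up: event.
- SAP 7.8.1 text: Day 1 censoring only for patients with no post-baseline response assessment, and not if they died without extended loss to follow-up.

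No order of precedence is given. To show the size if the first row prevails, assume exponential PFS with a median of 6.0 months in measurable patients. If non-measurable patients have the same hazard, the median does not move and only information is lost. If they are 10% of patients with a hazard ratio of 0.5 or 2, the all-patient median is 6.4 or 5.6 months, against 6.0 after dropping them; at 20%, it is 6.8 or 5.2.

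**6. DOR under the first-row reading.** SAP 7.8.1 computes DOR as (event or censoring date − response date + 1)/30.4375. Take a patient with at least 30% marrow plasma cells at baseline, a marrow-based PR on Day 57 (illustrative) and a Day 1 censoring date: 1 − 57 + 1 = −55 days, or −55/30.4375 = −1.8 months.

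**The case against.** The strongest reply has four parts.

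**These patients can respond.** A reader might infer that every non-measurable patient is a certain non-responder. Appendix F does not support that. Its CR definition has no measurable-baseline condition. VGPR can be met with M-protein seen on immunofixation but not on electrophoresis. A note there requires serum and urine studies for sCR, CR and VGPR whether or not baseline disease was measurable. PR is open at 30% marrow or more. Dilution is therefore probable, not certain.

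**Day 1 censoring is only one reading.** A reader might infer that every such patient is censored at first dose even after death or progression. The text of 7.8.1 and two rows of Table 1 point the other way. The negative DOR likewise needs the first row to override the text. This objection stands, but it leaves an unresolved conflict in the SAP.

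**CBR and DCR.** The synopsis lists them without the restriction, so the safety set agrees with one of the protocol's two versions. For DCR, a non-measurable patient with stable disease counts as a success, so the bias need not be downward. This stands: the two versions need reconciling.

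**Low stakes.** These are descriptive secondary endpoints, and SAP 7.4 tabulates a non-measurable category. That limits the severity. However, SAP 7.1.1 presents baseline data by schedule and efficacy by dose level, so the table would not show which ORR cell is affected.

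The protocol sentence calling all dosed patients evaluable for efficacy sits under Part 2 in Section 13.1.3 and does not override the Part 1 endpoint.

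**Conclusion.** The ORR, DOR and TTR populations in SAP 7.8.1 contradict the Part 1 endpoint definitions. For PFS, the first row of Table 1 conflicts with the endpoint, with the 7.8.1 text and with other rows of the same table. Both points should be corrected.

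The size is unknown because the number of non-measurable patients is not given; if it is zero, nothing changes. One non-measurable non-responder in a Q4W escalation cell would mean an ORR of 29% instead of 33%, or 20% instead of 25%. These figures assume that such a patient was in the cell and did not respond. PFS would be biased for the all-patient population only if the first row is applied and these patients' hazard differs.

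Two stronger conclusions are tempting. One is that the ORR and PFS estimates are simply wrong: the documents show a mis-specification that takes effect only if such patients were enrolled. The other is that the first row of Table 1 also distorts Parts 2 and 3, because baseline is the last pre-dose value and a repeat Cycle 1 Day 1 sample could fall below threshold. Both parts require measurable disease at entry, and nothing in the documents indicates that this happened or how often it would. The supported reach is Part 1 secondary endpoints and pooled Part 1 plus Part 2 summaries, with at most a one-responder shift in the second 120 mg futility boundary under the assumptions above.

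**What to change.** - **SAP 7.8.1:** for Part 1, analyse ORR, DOR and TTR in safety-set patients with measurable disease at baseline, using the classification in SAP 7.4. Keep the all-treated ORR as supportive. Report the number of non-measurable patients per dose level.
- **CBR and DCR:** choose one Part 1 population and align the synopsis, Protocol 5.4.1.2, SAP 5.1.2 and SAP 7.8.1.
- **SAP Table 1:** limit the first row to patients with no baseline disease assessment of any kind, or exempt Part 1 patients with baseline marrow or plasmacytoma disease. State that confirmed PD, or death without extended loss to follow-up, takes precedence over that row.

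The cost is SAP wording and minor programming, plus a protocol clarification for CBR and DCR if the synopsis is the text that changes. No new data are needed. The downside is a slightly smaller Part 1 ORR denominator and so slightly wider intervals.
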